### 2.2.3 Pharmacoeconomic variables

- Direct costs (healthcare provider consultations not foreseen by the protocol, concurrent medical procedures, concomitant medications, hospitalizations, and emergency room [ER] visits) during the first 2 years of the Evaluation Period
- Indirect costs (workdays or schooldays lost by the subject and days subject received help from a caregiver) during the first 2 years of the Evaluation Period
- Socio-professional data for each assessment for the first 2 years and for the last assessment during the first 2 years of the Evaluation Period

### 2.2.4 Pharmacokinetic variables

- Brivaracetam (parent compound only) plasma levels
- Concomitant antiepileptic drugs (AEDs) (and/or relevant metabolites) plasma levels

## 2.3 Study Design and Conduct

This is an open-label, long-term follow-up, multicenter, multinational, noncomparative, single-arm study of BRV. The primary objective is to evaluate the long-term safety and tolerability of BRV at individualized doses up to a maximum of 200mg/day in subjects suffering from epilepsy. The secondary objective is to evaluate the maintenance of efficacy over time of BRV. Exploratory objectives are to assess the effects of BRV on subjects' Health-Related Quality of Life (HRQoL), obtain information on the direct and indirect costs and subjects' self-reported health status.

At the time of development of this SAP, the enrollment into N01315 had completed. Study N01315 enrolled subjects 16 years of age and older who had completed N01276 or N01306.

Subjects who enrolled in the study entered an Evaluation Period at a recommended starting dose of 100mg/day. The dose of BRV could then be adjusted based on the individual subject's seizure control and tolerability. Dose increases could be made in increments of a maximum 50mg/day on a weekly basis and up to a maximum dose of 200mg/day; dose decreases could be made in steps of maximum 50mg/day on a weekly basis with a last down-

titration step at 20mg/day for 1 week. Subjects who completed the Down-Titration Period or subjects who discontinued during the Evaluation Period without entering the Down-Titration Period enter a Study Drug-Free Period for a minimum of 2 weeks and a maximum of 4 weeks. The maximum allowable daily dose for this study was increased from 150mg/day to 200mg/day based on integrated amendment 2 to the protocol. The daily dose should have been administered in 2 equal intakes (morning and evening), taken with or without food.

Subjects entering N01315 on BRV monotherapy could have converted to adjunctive BRV treatment during the N01315 study. In this case, as well as for subjects entering N01315 taking BRV and a concomitant AED, the Investigator may have adapted the concomitant AED drug/dosage for safety or efficacy reasons. In case of excellent efficacy and tolerability of BRV, withdrawal of concomitant AED(s) resulting in monotherapy with BRV may have been re-attempted by the Investigator.

Study visits at Months 2, 6, 12, 18, 24, etc., are either Full Evaluation Visits (FEVs) or Yearly Evaluation Visits (YEVs) at which a greater number of assessments are performed. Study visits at Months 1, 3, 9, 15, 21, etc. are Minimal Evaluation Visits (MEVs) at which few assessments are performed. If a subject elected to end their study participation prior to study completion, then an Early Discontinuation Visit was conducted and subjects were progressively down-titrated from study medication. Once study medication down-titration was completed, a telephone call was conducted for subjects who discontinued taking more than BRV 20 mg/day. A Study Drug Free Period was initiated after down titration of study medication was completed. The Final Visit was conducted after the Study Drug Free Period. The Visit schedule described is displayed in [Table 2-1](#).

**Table 2-1: Visit Schematic Diagram**

| 1 st , 2 nd and subsequent years follow-up |       |                  |
|--|-------|------------------|
| Month  | Visit | Type of Visit    |
| M0   | V1    | Entry Visit (EV) |
| M1   | V2    | MEV              |
| M2   | V3    | FEV              |
| M3   | V4    | MEV              |
| M4   |       |                  |
| M5   |       |                  |
| M6   | V5    | FEV              |
| M7   |       |                  |
| M8   |       |                  |

**Table 2-1: Visit Schematic Diagram (Continued)**

| 1 st , 2 nd and subsequent years follow-up |       |               |
|--|-------|---------------|
| Month  | Visit | Type of Visit |
| M9   | V6    | MEV           |

| 1st, 2nd and subsequent years follow-up |              |                      |
|--|--------------|----------------------|
| Month   | Visit | Type of Visit |
| M10  |              |                      |
| M11  |              |                      |
| M12  | V7           | YEV                  |
| M15  | V8           | MEV                  |
| M18  | V9           | FEV                  |
| M21  | V10          | MEV                  |
| M24  | V11          | YEV                  |
| M...   | V...         | ...                  |

FEV=Full Evaluation Visit; MEV=Minimal Evaluation Visit; M=month; V=visit; YEV=Yearly Evaluation Visit

Visit 1 will correspond to the last visit from the previous study and should be the visit at which study drug is dispensed for N01315.

This study will run throughout the duration of the clinical development period of BRV, and will continue until a marketing authorization is granted by any Health Authority in an indication for the adjunctive treatment in adults with refractory POS, whether or not secondarily generalized, until the Sponsor decides to close the study, or until BRV development is stopped by the Sponsor.

## **2.4 Determination of Sample Size**

No sample size calculation was done. Sample size was dependent upon recruitment into and completion of preceding studies. At the time of development of this SAP, the enrollment into this study has been completed and a total of 108 subjects have been enrolled into N01315.

## **2.5 Changes from the Analysis Planned in the Protocol**

Percentage of subjects remaining on continuous BRV monotherapy from the start of the study through 3, 6, and 12 months will not be done because it would be limited to subjects entering on monotherapy and it was expected that this rate would be low due to the parent studies being stopped prematurely. Instead of this analysis, the cumulative proportion of subjects able to achieve BRV monotherapy for 3, 6, and 12 months during the Evaluation Period will be summarized.

# **3 DATA ANALYSIS CONSIDERATIONS**

## **3.1 General Presentation of Summaries and Analyses**

Statistical analysis and generation of tables, figures, subject data listings, and statistical output will be carried out using SAS® Version 9.1 or higher.

Descriptive statistics, such as the mean, standard deviation (SD), median, 25th percentile, 75th percentile, minimum value, and maximum value for quantitative variables, and counts and percentages for categorical variables, will be provided. Denominators for percentages will

generally be based on the set of subjects with at least 1 assessment at the time point or at least 1 assessment during the time interval being summarized.

All summaries will be descriptive; no statistical hypothesis testing is planned.

Unless otherwise noted, summaries will present BRV overall, which will include all subjects exposed to BRV during the study.

Subject data listings will be provided and will present source data and key derived variables for statistical analyses.

## **3.2 Analysis Time Points**

### **3.2.1 First and last dose of BRV**

Unless otherwise noted, all references to the first dose of BRV in this SAP refer to the first dose of BRV during N01315. Unless otherwise noted, all references to the last known dose of BRV in this SAP refer to the last dose of BRV taken across any study periods (ie, not necessarily the last dose of BRV during the Evaluation Period).

### **3.2.2 Relative day**

Relative day will be calculated as the current date minus the date of first dose of study drug for days prior to the first dose of study drug, and the current date minus the date of first dose of study drug plus 1 for days on or after the day first dose of study drug and prior to or on the day of last study drug dose (eg, the day of first dose will be Day 1 and the day prior to first dose will be Day -1), ie, Day 1 representing the day of first dose of BRV, the previous day is Day -1 and each day prior to that is Day -2, Day -3, etc; subsequent relative days to Day 1 will be Day 2, Day 3, etc. For days after the last dose of BRV, relative day will be calculated as the current date minus the date of last dose of BRV and including a '+' to denote post treatment days (eg, the day after the last dose of BRV will be Day +1). Relative day will not be calculated for partial or missing dates.

### **3.2.3 Summaries at Study Entry**

The study Entry Visit (EV) corresponds to assessments performed at the time of entry into N01315. There are 2 groups of subjects to consider:

1. Subjects who immediately entered N01315 after completing the Evaluation Period or meeting the protocol defined exit criteria for N01276 and N01306
2. Subjects who did not immediately enter N01315 and had a gap in treatment with study drug between the previous study and N01315

Subjects in category 1 will generally not have any interruption in study drug dosing during the transition to N01315. Subjects in category 2 had minimal gaps in treatment, which will not change how the data are analyzed. For subjects in both categories, selected assessments from Visit 8 of the previous study will be summarized at EV. Subjects who met exit criteria in the prior study will have data from EDV used as EV for N01315.

For the assessments that were performed for all subjects at Visit 8/EDV of the previous study, the following assessments will be summarized at EV: vital signs, weight, physical examination, neurological examination, ECGs, recording of seizures, and laboratory parameters.

### 3.2.4 Study periods

The study is divided into 3 periods: Evaluation Period, Down-Titration Period, and Post-Treatment Period. A subject is classified as “discontinued” if the subject has a termination case report form (CRF) or has an early discontinuation visit (EDV). A subject is classified as “completed” if this subject completes the full extent of the study as defined in the protocol at database lock.

A “discontinued” subject can be potentially slotted into the 3 periods of the study. The following algorithms will be used to slot the subject appropriately into the Evaluation Period, Down-Titration Period, and Post-Treatment Period.

- For Evaluation Period, the start date is the date of first dose of BRV, and the following algorithm is used to determine the end date:
  - If the subject enters the Down-Titration Period, then the date of EDV is the end date;
  - If the subject does not enter the Down-Titration Period but meets 1 of the following criteria, the Evaluation Period ends on date of last dose of BRV:
    - Without an EDV but having a termination CRF,
    - With an EDV and having a termination CRF,
    - With an EDV and the date of EDV prior to the database lock date and having no termination CRF.
- A subject is considered entering Down-Titration Period only if the subject has an EDV and at least 1 dose of study drug after the date of EDV, the start date of Down-Titration Period is set as 1 day after the date of EDV, and the Down-Titration Period ends on date of last dose of BRV. A subject without an EDV but having a termination CRF or with an EDV but without any dosing of study drug after the EDV will not have the Down-Titration Period, and no artificial Down-Titration Period will be created for analysis.
- A subject is considered entering the Post-Treatment Period if the subject has at least 1 contact (scheduled visit, unscheduled visit, or telephone contact) after the date of last dose of BRV. The Post-Treatment Period starts 1 day after date of last dose of BRV irrespective of entering the Down-Titration Period, and there is no end date.

A “completed” subject can potentially have Evaluation Period, Down-Titration Period, or Post-Treatment Period. At the time of study termination by the Sponsor, subjects will discontinue the study drug following the down titration process or will be converted without titration to commercial BRV where available; alternatively, subjects may be initiated without down-titration in a managed access program, named patient program, compassionate use program, or similar type of access program as allowed per country specific requirements in addition to legal and regulatory guidelines.

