- ⁽ⁱ⁾ End of study status will be completed at the FV for subjects having performed an EDV (discontinued subjects) and for subjects leaving the study at the end of the program (completed subjects).
- ^(j) The C-SSRS assessment will be implemented by site per IRB/IEC approval upon completion of required training. As of the time of Protocol Amendment 2, all subjects had completed their EV. Thus, the C-SSRS was not assessed for any subjects at their EV.
- ^(k) Procedures only performed during the first 2 years of subject participation in the study or EDV/FV in case the subject discontinues participation within the first 2 years.
- ^(l) For subjects that may transition to another BRV study or a managed access program or similar type of program, the EDV will need to be completed, however down-titration and FV may not be applicable.

This document cannot be used to support any marketing applications and all dimensions or variations thereof.

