8.4 Study Duration

This study will run throughout the duration of the clinical development period of BRV, and will continue until a marketing authorization is granted by any Health Authority in an indication for the adjunctive treatment in adults with refractory POS, whether or not secondarily generalized, until the Sponsor decides to close the study, until subjects transition to another BRV study, until a managed access program, named patient program, compassionate use program, or similar type of access program is established as allowed per country-specific requirement in addition to legal and regulatory guidelines, or until BRV development is stopped by the Sponsor.

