## 5 STUDY POPULATION CHARACTERISTICS

### 5.1 Subject Disposition

Due to differences in data format across studies, in order to facilitate summary of subject disposition, the reasons for discontinuation for individual studies will be collapsed as follows for summaries:

| LTFU Category     | CRF Reason  |
|-------------------|---|
| ADVERSE EVENT     | ADVERSE EVENT   |
| LACK OF EFFICACY  | LACK OF EFFICACY  |
|                   | LOSS OF EFFICACY  |
| LOST TO FOLLOW-UP | LOST TO FOLLOW-UP   |
| SUBJECT CHOICE    | CONSENT WITHDRAWN   |
|                   | WITHDRAWAL OF CONSENT FOR PERSONAL REASONS NOT RELATED TO AES                     |
|                   | WITHDRAWAL OF CONSENT FOR PERSONAL REASONS NOT RELATED TO AES OR LACK OF EFFICACY |
| OTHER             | PROTOCOL VIOLATION  |
|                   | OTHER REASON  |
|                   | OTHER   |
| MISSING           | If subject discontinued the study and the termination CRF is not available        |

Only 1 primary reason for discontinuation should have been reported. In the event that more than 1 reason is specified in the clinical database, both reasons will be summarized and a footnote will be added to the summary table to indicate that at least 1 subject is counted for multiple reasons for discontinuation.

An overall summary of disposition will be provided for all enrolled subjects (ie, all subjects who signed informed consent). The following will be summarized:

- The number of subjects in the Safety Analysis Set
- The number of subjects excluded from the Safety Analysis Set
- The number of subjects completed the study
- The number of subjects who have discontinued from the study, including the reason for discontinuation. If subject discontinued the study and the termination CRF is not available, the reason for discontinuation will be reported as “MISSING”.

Additionally, an overall summary of disposition will present the following for subjects in the Safety Analysis Set:

- The number of subjects completing the study The overall number of subjects discontinuing and the number of subjects discontinuing by primary reason for discontinuation. If subject discontinued the study and the termination CRF is not available, the reason for discontinuation will be reported as “MISSING”.

Overall subject disposition will also be summarized by geographic region for the Safety Analysis Set.

The number of subjects within each geographic region will be summarized for the Safety Analysis Set.

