Kaplan-Meier estimates of the percentage of subjects completing 3, 6, 12, 24, 36, 48, and 60 months of treatment with BRV will be provided. This analysis will be based on the duration of exposure to BRV as defined in Section 3.2.7. Subjects who have permanently discontinued will be analyzed as events on the last day of treatment with study drug; subjects who complete the study will be censored on the last day of treatment with study drug.

The date of first subject in (date of earliest Visit 1), date of last subject out (date of last scheduled or unscheduled visit), number of enrolled subjects, and the number of subjects in each analysis set or indication will be summarized overall and by investigator site. Subjects who transferred sites will be summarized according to their original site.

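### An early discontinuation visit alone makes a subject 'discontinued' in the SAP, yet the protocol requires that visit of subjects who transfer to other BRV access and stay on drug; how they enter the retention curve is not settled

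*SAP*

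**What the plan says.** **Classification.** Under SAP 3.2.4 a subject is discontinued "if the subject has a termination case report form (CRF) or has an early discontinuation visit (EDV"). Either one is enough, and no exception is made. A subject is completed on going through the whole study as the protocol defines it. For completed subjects at Sponsor termination the section lists down-titration and commercial BRV, and adds: "alternatively, subjects may be initiated without down-titration in a managed access program". It does not mention another BRV study, which protocol 10.1.1.1 and 11.1.24 do.

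**The visit.** Protocol Table 5:1, footnote (l), says that for subjects who may "transition to another BRV study or a managed access program or similar type of program, the EDV will need to be completed". It adds that down-titration and the Final Visit may not apply to them. Footnote (i) places the end-of-study status at the Final Visit. It labels subjects with an EDV as discontinued and those leaving at the end of the program as completed.

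**The protocol's outcomes.** Protocol 11.1.24 has two: completed, meaning that the subject took part until the study was stopped, and prematurely discontinued.

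**Duration.** Protocol 8.4 lists among the study's end points "until subjects transition to another BRV study, until a managed access program" or similar is set up. The matching text in SAP 2.3 closes with "until the Sponsor decides to close the study, or until BRV development is stopped by the Sponsor" and leaves those routes out.

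**Analysis.** SAP 5.1 plans Kaplan-Meier percentages completing 3 to 60 months of BRV treatment. Its event rule reads: "Subjects who have permanently discontinued will be analyzed as events on the last day of treatment with study drug". Censoring is provided for one group only: "subjects who complete the study will be censored on the last day of treatment with study drug". Its reason table has no transfer category. For an absent form it says "If subject discontinued the study and the termination CRF is not available, the reason for discontinuation will be reported as" and then names the MISSING category.

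**The concern.** The EDV does two jobs. In the protocol it is a procedure that some subjects must go through on the way to further BRV. In the SAP it is a marker that the subject stopped. A subject who transfers and keeps taking BRV can therefore be scored as having left treatment, on a curve meant to show how long subjects stay on BRV. The same subject's reason for leaving would sit in a catch-all row.

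The study's primary objective is long-term safety and tolerability, and retention and disposition are among the outputs read for tolerability. Nothing in the SAP suggests that this case was considered and decided. The transition routes are absent from its duration text, another BRV study is absent from its list of routes at closure, and SAP 2.5 records no decision.

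**Working it through.** The plan states no retention figure, so there is none to reproduce. The check has two parts.

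**1. Follow each kind of subject through the rules.**

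- *Moves before closure and stays on BRV.* Footnote (l) requires an EDV, so SAP 3.2.4 gives 'discontinued'. Under protocol 11.1.24 the subject did not take part until the study was stopped. SAP 5.1 offers only event or completer censoring, so the natural result is an event at the last dose. If protocol 8.4 is read as ending the study for each subject at transition, the subject also meets 'completed', and there is no tie-break.
- *Moves at Sponsor closure to another BRV study or an access program.* Protocol 11.1.24 gives 'completed', as SAP 3.2.4 does for access programs. If an EDV is done, SAP 3.2.4 also gives 'discontinued'. No precedence is stated.
- *Converts to commercial BRV at closure.* No text requires an EDV, and protocol 11.2.7 provides a Final Visit at the end of the program. The conflict arises only if an EDV or a termination CRF is completed.
- *Disposition row.* A mover classed as discontinued goes to OTHER, or to MISSING without a termination CRF. The second is possible because the status page is tied to a Final Visit that movers may not have, and SAP 3.2.4 itself foresees an EDV with no termination CRF.

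**2. Bound the effect on retention.**

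Inputs: n dosed subjects, at most the 108 enrolled (SAP 2.4); K movers and W true withdrawals before month t; no completer censored before t. The documents do not give K, W or the timing.

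- Movers as events: S = 1 − (W + K)/n.
- Movers censored: each withdrawal lowers S by S/r, with r at risk. S/r starts at 1/n, is unchanged by a withdrawal and rises with each censoring. So each fall is at least 1/n, and S ≤ 1 − W/n.
- The gap is therefore at most K/n. With n = 108 that is 0.93 points for K = 1, 1.85 for K = 2, 3.70 for K = 4 and 9.26 for K = 10. If only 100 were dosed (an assumption), it is 1.00 point each.

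For one mover with r at risk and w later withdrawals, the gap is exactly (r − 1 − w)/[n(r − 1)]. With n = 108 and assumed r = 80, w = 10: censored 80/108 × 69/79 = 64.70%, event 69/108 = 63.89%, gap 0.81 points. For one move at month 36, the expected gap at month 60 is about (100/108) × exp(−2h) points. That is 0.84 at an assumed withdrawal rate h = 0.05 per year and 0.51 at h = 0.30.

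Illustration with n = 108, assuming 60 withdrawals spread evenly over months 1 to 60 and 10 movers spread evenly over months 24 to 48, with everyone else followed past month 60. Month-48 retention is (108 − 48 − 10)/108 = 46.3% with movers as events and 53.9% with movers censored. The gap is 7.6 points, inside the bound of 9.26. Before the first move the two curves are identical.

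Once completers are being censored, the bound no longer holds. One event then costs S/r: 60%/40 = 1.5 points, or 60%/20 = 3.0 points, both at assumed values.

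In the disposition table, each mover classed as discontinued adds 1/108 = 0.93 percentage points to that count.

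**The case against.** The strongest reply has five parts.

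- *Transition is described at closure.* Protocol 10.1.1.1 and 11.1.24 both place it at study termination by the Sponsor, and those subjects are completers. This largely stands. For them the fault is two overlapping classes without precedence, not a plain misclassification. Footnote (l) and protocol 11.2.5 set no timing, though, and protocol 8.4 leaves room for earlier moves.
- *SAP 5.1 does not cite 3.2.4.* Its term, 'permanently discontinued', is undefined, and the stated use of the 3.2.4 class is to assign subjects to study periods. This stands as a limit. A reader might infer that the SAP explicitly makes movers events. It does not; that is the natural reading, because completion is the only alternative offered.
- *In-study retention is a legitimate target.* SAP 3.2.1 and 3.2.7 measure dosing in this study, so leaving it could count as an event. But completers who go on to commercial BRV or an access program also end their dosing in this study, and they are censored. The SAP already treats leaving the study while staying on BRV as a non-event at closure. What stands is that censoring movers may be informative, which is why both curves are wanted.
- *Movers do have a disposition row.* Correct. A reader might infer that they drop out of the table, but OTHER exists and protocol 9.3 has an other reason specified in the CRF. What is lost is a row of their own.
- *Protocol 13.5 plans a pre-lock review that covers withdrawals.* It is the right place to settle single cases, but it states no rule.

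**Conclusion.** The mismatch is firm on the text: the protocol requires an EDV of movers, and the SAP makes an EDV sufficient for 'discontinued'. The consequence is held with moderate confidence. It depends on reading 'permanently discontinued' as the 3.2.4 class, and on there being subjects who move and keep taking BRV.

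The number of movers is not given and may be zero, in which case nothing changes. Otherwise retention is lowered by at most K/n before completers are censored, or 0.93 points per mover if all 108 enrolled subjects were dosed. It can be more per mover afterwards. It would be tempting to conclude that the long-term retention figures are materially biased, but the documents give no count or timing that would support this.

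The outputs are descriptive, with no testing. The three primary safety variables (TEAEs, withdrawal due to AE, SAEs) are not affected. The point is worth fixing before database lock because a stated rule can give a wrong answer and the correction is a matter of wording.

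**What to change.** 1. **SAP 3.2.4.** State that 'completed' (took part until the study was stopped, protocol 11.1.24) takes precedence over the presence of an EDV or a termination CRF. State that an EDV or termination CRF done only for transfer to other BRV access does not by itself make a subject permanently discontinued. The existing period-end rules can be applied to movers as they are.
2. **SAP 5.1, Kaplan-Meier.** Define the event as permanent discontinuation other than transfer to other BRV access. Censor completers and movers at their last dose in N01315. Add transfer-as-event as a sensitivity analysis, because censoring movers may be informative.
3. **SAP 5.1, disposition.** Show transfers as a separate line or sub-reason.

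The cost is a few sentences, one table line and one extra curve, with no new data collection. The main burden is checking the reason behind every EDV and termination form, since movers may have a Final Visit, a termination form, both or neither. That fits within the pre-analysis review already planned in protocol 13.5.
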